# 3. Assessment of Efficacy

### 3.1 Primary Outcome Measure

This study will compare the primary outcome of mean eGFR between the standard q-1M control group and the q-2M treatment group, with the hypothesis that mean eGFR will not vary between the groups by more than a pre-specified acceptable difference, or equivalence margin. Difference in eGFR between the q-1M and q-2M treatment groups will be assessed monthly.

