# 7. Study design and methods

After randomization into either the q-1M or q-2M dosing groups, belatacept will be administered at a dose of 5 mg/kg, the same dose the patient was taking at the beginning of the study. The visit window for the q1M group will be per standard of care and the visit window for the q2M group will be +/- 5 days. See the attached dosing schedule and budget for the schedule of drug administration and lab tests. Q-2M patients will have lab tests every two weeks starting at week 4 of the study (the first time point when the q-1M patients receive belatacept and theq-2M patients do not). The q-2M group will have labs performed every two weeks from week 4 through week 16. With the exception of every two week labs for the q-2M group from week 4 through week 16 and frequency of belatacept administration, both groups of patients will be treated the same in all ways. Labs will be monthly otherwise. For study purposes, patients will receive a chemistry profile at every lab draw and antibody assessment (PRA/DSA) labs at enrollment, and 6 and 12 months. Otherwise they will be managed per standard of care as clinically indicated. For mechanistic studies, blood and serum will be drawn and stored on select study patients.

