# 9. Study Procedures and Assessments

# See Appendix 3.

# 10. Statistical Analysis

All analyses will be conducted on the intent-to-treat (ITT) population. The distribution of continuous outcome measures will be examined, and non-parametric equivalents of the two-sample t-test will be used to assess the statistical significance of non-normally distributed outcomes.

Statistical significance of the mean difference in eGFR between the q-4 and q-8 treatment groups at 12 months post-randomization will be assessed using the two-sample independent t-test statistic. The incidence of clinically suspected or biopsy-proven acute rejection (and date of acute rejection) will be collected based upon final ETC biopsy-proven acute rejection. We will describe acute rejection rates at 6 and 12 months post-randomization for the overall cohort and for the q-1M and q-2M treatment groups by calculating time to acute rejection. Kaplan-Meier analyses examining time to acute rejection will be used for comparisons by treatment group, with the log-rank test used to assess statistical significance. Potential differences in the severity of acute rejection between the treatment groups will be assessed by comparing the proportions of grade IIA and lower rejections and grade IIB and higher rejections between the treatment groups. Statistical significance of acute rejection severity will be assessed using the two-sample independent t-test statistic.

The incidence of infection in the q-4 and q-8 treatment groups will be collected based on labs performed at regular intervals throughout the study duration. Differences in the incidence of infection by treatment group will be assessed using the two-sample t-test statistic. The incidence of death and graft loss will also be determined, and the death rate and graft loss rates will be calculated at 6 and 12 months post-randomization. Kaplan-Meier analyses examining time to death and time to graft loss will be used for comparisons by treatment group, with the log-rank test used to assess statistical significance.

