The mean eGFR at one year post-transplant for patients receiving belatacept at the Emory Transplant Center has been found to be 60.2 ml/min/1.73 m² with a standard deviation of 14.5 ml/min/1.73 m². When patients with an eGFR less than or equal to 35 ml/min/1.73 m² are excluded, the mean eGFR at one year post-transplant has been found to be 61.5 ml/min/1.73 m² with a standard deviation of 13.1 ml/min/1.73 m². Based on this inclusion criterion, the table below details several scenarios of potential sample size for different equivalence margins in order to attain 80% power for a significance level (alpha) of 0.05.

Calculated GFR is a continuous variable and will be assessed at monthly intervals (increasing to every two weeks from week 4 to 16 in the q-2M group) throughout the study. The secondary time points of rejection, death, graft lost, and HLA antibody production will be assessed at 6 and 12 months. Total cost, clinic visits, hospitalizations, biopsies and patient satisfaction will be assessed at 12 months.

Assuming a standard deviation of 13.1 ml/min/1.73 m^2:

Equivalence margin	N per group	Sample Size (total
(ml/min/1.73 m  )		N)
5.0	119	238
5.5	98	196
6.0	83	166
6.5	71	122
7.0	61	122

For example, assuming the standard deviation for eGFR at one year post-transplant is 13.1 ml/min/1.73 m^2, 166 patients total (83 per treatment group) are required to be 80% sure that a

two-sided 95% confidence interval will exclude a difference in mean eGFR between the treatment groups of more than 6.0 ml/min/1.73 m^2.

This study also aims to compare the secondary outcome of acute rejection rate between the q-1M and q-2M dosing interval groups. The one-year post-transplant acute rejection rate among patients treated with belatacept is expected to be 1-2%; based on this assumption, the table below details several scenarios of potential sample size for absolute differences in acute rejection rate in order to attain 80% power for a significance level of 0.05.

AR rate for reference group	AR rate for intervention group	Absolute difference	N per group	Sample Size
(q-4)	(q-8)	difference		(total N)
1%	4%	3%	137	274
1%	5%	4%	77	154
1%	6%	5%	49	98
1%	8%	7%	25	50
2%	5%	3%	270	540
2%	7%	5%	97	194
2%	8%	6%	68	136
2%	9%	7%	50	100

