#### The DSMB will:

- Protect the welfare of the patient.
- Monitor interim safety data.
- Identify safety issues and suggest solutions regarding study design and conduct.
- Review the study protocol and any protocol amendments
- Review the methods of data collection and safety monitoring making recommendations for additions or adjustments to ensure the timely delivery of such data.

- Review and approve the DSMB charter that defines the safety and related parameters to be reviewed by the DSMB, the frequency of DSMB monitoring reviews, methods for review, and establish criteria for making recommendations to the principal investigator.
- Conduct a futility analysis based at the time when approximately 30% of the study subjects complete the 6-month data collection.
- Based on the data reviewed at each meeting, the DSMB will advise one of the following actions to the principal investigator:
  - Continue the study according to the protocol and any related amendments.
  - Modify the study protocol. Modifications may include, but are not limited to: changes in inclusion/exclusion criteria, frequency of visits or safety monitoring, and alterations in study procedures.
  - Discontinue the study overall or end participation in particular subgroup.

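### The primary 12-month eGFR comparison ignores the baseline eGFR already collected in both arms; adjusting for it would probably narrow the interval set against the 6.0 margin, at almost no cost

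*Combined protocol and SAP*

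**What the plan says.** - **Primary test.** Section 10 compares mean eGFR between arms "at 12 months post-randomization will be assessed using the two-sample independent t-test statistic". For skewed data, "non-parametric equivalents of the two-sample t-test will be used to assess the statistical significance of non-normally distributed outcomes". Section 10 mentions no baseline covariate, change score, stratification by eGFR or repeated-measures model.
- **Success criterion.** In Section 10, 83 patients per arm are meant to give 80% assurance that a "two-sided 95% confidence interval will exclude a difference in mean eGFR between the treatment groups of more than 6.0" ml/min/1.73 m². The SD used is 13.1, a cross-sectional value after excluding eGFR of 35 or less. The SD without that exclusion is also given: "with a standard deviation of 14.5".
- **Baseline data.** Section 7 states that "patients will receive a chemistry profile at every lab draw", and the Schedule of Events marks the basic chemistry panel at M0 in both arms. Section 8.2 excludes patients with GFR below 35, so GFR must be known at entry.
- **When the arms diverge.** Section 7 identifies week 4 as "the first time point when the q-1M patients receive belatacept and theq-2M patients do not".
- **Access to eGFR by arm.** Section 3.1: "Difference in eGFR between the q-1M and q-2M treatment groups will be assessed monthly". The DSMB charter adds an interim look: "Conduct a futility analysis based at the time when approximately 30% of the study subjects complete the 6-month data collection".

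**The concern.** The trial concludes in favour of two-monthly dosing only if the interval for the eGFR difference stays within 6.0, so the width of that interval matters as much as the point estimate. Part of the spread in 12-month eGFR is difference between patients that was already there at M0. An unadjusted t-test leaves that spread in the standard error; ANCOVA removes the part that M0 eGFR predicts.

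On the basis that reproduces the planned sample size there is almost no reserve. At 83 per arm power is 80.4%, at 82 it is 79.8%, and the step from 200 consented to 166 randomized in Section 8 covers screen failure only. A covariate already collected is the cheapest source of reserve. At stake is a wider interval than necessary, and so a greater chance of an inconclusive trial when the two schedules are in fact alike.

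**Working it through.** **Inputs.** From Section 10: SD 13.1, margin 6.0, 83 per arm, 80% power. Assumed: true difference 0; M0 and 12-month eGFR jointly normal; r from 0 to 0.7, because the documents give no value.

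**Step 1: reproduce the plan's sample size.** Equivalence power with a true difference of 0 is the average of max{0, 2Φ(6/SE − t·√(u/df)) − 1} over u, where u is chi-square on df degrees of freedom, SE = SD·√(2/n) and t is the one-sided critical value. At one-sided 0.05 (a 90% interval) and 80% power, the smallest n per group is 119, 98, 83, 71 and 61 for margins 5.0, 5.5, 6.0, 6.5 and 7.0. These match every N per group in the Section 10 table. The two-sided 95% interval named in the text would need 102 per group at margin 6.0. Results are therefore shown for both levels.

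**Step 2: unadjusted t-test.** SE = 13.1 × √(2/83) = 2.034 on 164 df. The 90% half-width is 1.654 × 2.034 = 3.36.

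**Step 3: ANCOVA on M0 eGFR.** The residual SD is 13.1 × √(1 − r²), df is 163, and the variance is multiplied by 1 + 1/162 to allow for chance imbalance in the covariate. At r = 0.5 the residual SD is 11.34 and SE = 11.34 × √(2/83) × √(1 + 1/162) = 1.767. The 90% half-width is then 1.654 × 1.767 = 2.92.

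| Analysis | 90% half-width | Power, 90% CI within ±6.0 | Power, 95% CI within ±6.0 |
|---|---|---|---|
| Unadjusted | 3.36 | 80.4% | 67.0% |
| ANCOVA, r = 0 | 3.37 | 80.1% | 66.5% |
| r = 0.1 | 3.36 | 80.6% | 67.2% |
| r = 0.2 | 3.31 | 82.1% | 69.4% |
| r = 0.3 | 3.22 | 84.6% | 73.1% |
| r = 0.5 | 2.92 | 91.8% | 84.3% |
| r = 0.7 | 2.41 | 98.6% | 96.7% |

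A simulation of 100,000 trials at each r agreed with the 90% column to within about 0.2 percentage points.

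**Step 4: break-even.** ANCOVA gains once (1 − r²)(1 + 1/162) < 1, that is r² > 1/163, or r above about 0.08.

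**Step 5: other readings.** As a non-inferiority test at one-sided 0.025, power is 83.5% unadjusted, and 84.7%, 86.6%, 92.2% and 98.4% at r = 0.2, 0.3, 0.5 and 0.7.

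The SD of 13.1 comes from data cut at 35, whereas 12-month values are not cut. Taking 14.5 as an upper reference, 90%-interval power is 68.7% unadjusted, and 68%, 71%, 74%, 84% and 96% at r = 0, 0.2, 0.3, 0.5 and 0.7.

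**The case against.** The strongest reply is that this is a choice of method, not an error. The t-test is unbiased under randomization, its interval already allows for chance imbalance, and it matches a sample size built on an unadjusted SD. That stands, and it is why the point is a recommendation about efficiency and not a fault in validity.

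Second, the benefit rests on a correlation the documents do not supply. At r = 0.2 the gain is only 1.7 percentage points. The exclusion of GFR below 35 narrows the baseline range, and the undescribed handling of death and graft loss in 12-month eGFR could also weaken the correlation. This stands as to size. As to direction, the entry criteria point to a positive r: the same patients, at least a year post-transplant, with no rejection in the last six months and creatinine not more than 30% above its value three months before. That is an inference, not a documented figure.

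Third, the lack of reserve applies to the equivalence reading. Section 2.1 calls the trial non-inferiority, and on that reading at one-sided 0.025 unadjusted power is 83.5%. This is correct and softens the argument there. Under the 95% interval in the text, read as equivalence, the plan is weaker (67.0%) and adjustment is worth more. Which reading governs needs to be settled separately.

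Fourth, the time for a change may have passed. The document is Version 5.0 of 10 July 2018, Section 1 places the present at May 2015, and Section 8 projects two years. The documents do not state the trial's status, so the fix covers both situations.

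**Conclusion.** The concern holds. The primary analysis omits a baseline value that is already collected and unaffected by arm. Adjusting for it narrows the interval whenever r exceeds about 0.08. On the basis that reproduces 83 per arm, the gain is at most about 4 percentage points of power for r up to 0.3 (80.4% to 84.6%), and it is material from about 0.5 (91.8%, with an interval about 13% narrower: 2.92 against 3.36). The loss if r is 0 is 0.3 points on that basis and about 0.5 on the 95% equivalence basis. The direction is firm for any meaningful positive correlation; the size is unknown because r is assumed. The figures also rest on a true difference of 0, joint normality, SD 13.1 and complete 12-month data.

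**What to change.** In Section 10, before anyone who sets the analysis has seen an eGFR comparison by arm:

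1. Make the primary analysis an ANCOVA of 12-month eGFR on arm, with M0 eGFR as covariate.
2. State a rule for a missing M0 value, for example the last value before randomization.
3. Compare the confidence interval for the adjusted difference with the 6.0 margin, at whatever level the plan settles on.
4. Keep the unadjusted difference as a sensitivity analysis.
5. If residuals are clearly non-normal, use a robust or bootstrap interval for the same adjusted difference. The present non-parametric fallback tests only for a difference and is not tied to the margin.
6. Record the date of the change and who had seen eGFR by arm.

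If eGFR by arm has already been seen, leave the unadjusted interval as primary and report the ANCOVA as supporting.

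The cost is a few sentences and a documented change to the primary analysis, with no new data, visits or patients, and one degree of freedom (164 to 163). Timing is the real constraint: arm differences are to be assessed monthly, a futility analysis is planned and the documents describe no blinding, so a late change would cost credibility.

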Belatacept immunosuppressive therapy was implemented in the Emory Transplant Center (ETC) beginning in August of 2011. Current dosing protocol requires post-transplant kidney patients who are treated with belatacept to receive an infusion every 1 month, which presents logistical challenges due to the high cost of infusions, the limited capacity of the sites administering infusions, and inconvenience to patients. Definitive clinical evidence is lacking for equivalent treatment outcomes for patients who receive infusions at one month (q-1M) intervals versus every two month (q-2M) intervals. Data from five year (Vincenti F, Blancho G, Durrbach A et al. J Am Soc Nephrol 2010) and ten year (personal communication, [name]) follow up of the phase II clinical studies suggest that there are no significant differences in the patient outcomes for q-1Mversus q-2 Mdosing intervals. However, conclusions regarding differential

outcomes for the dosing interval regimens were limited by small sample size and deserve further investigation.

We hypothesize that immunologically low risk patients who are stable on belatacept therapy at least one year post transplant can be safely transitioned from an every 1 month to an every 2 months belatacept schedule, without a decrease in renal function or an increase in acute rejection. The Emory Transplant Center is uniquely qualified to perform this every two month study. We perform approximately 230 kidney transplants per year, utilizing belatacept as standard therapy in all eligible patients (Epstein Barr Virus (EBV) positive, etc). We have performed almost 500 kidney transplants on patients using belatacept as the primary immunosuppressant medication between August 2011 and the present (May 2015). Based on this clinical volume and high rate of belatacept use, we propose to screen approximately 18 patients per month and estimate enrolling an average of 12 patients per month into the study, specifically converting 6 patients per month from a q-1 month to a q-2 month schedule.

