# 8. Study Population

The trial population consists of adults ≥18 years of age who are first-time transplant recipients of either living donor or deceased donor renal transplants. Patients of all races and ethnicities will be included.

This is an intention to treat, randomized, controlled trial. There will be a total of 166 subjects, randomized in equal numbers, 83 patients in each arm. We anticipate needing to consent/enroll 200 patients to achieve 166 randomized subjects accounting for an approximate 15% screen failure rate. All patients will be actively followed in the study for 12 months following enrollment. The study is projected to last 2 years.

Before any study procedures are performed, the details of the study will be described to subjects, and they will be given a written informed consent document to read. Patients who consent to participate in the study will sign and date the informed consent document in the presence of study personnel. Only patients who have given informed written consent will be included in this study.

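### The acute rejection comparison rests on log-rank significance with no interval for the between-arm difference, so a non-significant result at 83 per arm cannot support the hypothesis of no increase

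*Combined protocol and SAP*

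**What the plan says.** Section 1 (Background and Rationale) hypothesises that stable, immunologically low-risk patients can move safely to the two-monthly schedule "without a decrease in renal function or an increase in acute rejection".

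Section 10 treats the two halves of that hypothesis differently. For eGFR it gives a margin of 6.0 ml/min/1.73 m² and a two-sided 95% confidence interval that should exclude a larger difference. For rejection it describes rates at 6 and 12 months, overall and by arm, and then states: "Kaplan-Meier analyses examining time to acute rejection will be used for comparisons by treatment group", "with the log-rank test used to assess statistical significance". Death and graft loss are handled in the same way: "Kaplan-Meier analyses examining time to death and time to graft loss will be used for comparisons by treatment group".

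On size, Section 8 has patients "randomized in equal numbers, 83 patients in each arm". Section 10 adds: "This study also aims to compare the secondary outcome of acute rejection rate". It gives the reference rate: "The one-year post-transplant acute rejection rate among patients treated with belatacept is expected to be 1-2" per cent. A table then lists eight pairs of rates for the two arms, presented as "absolute differences in acute rejection rate in order to attain 80% power for a significance level of 0.05". No row is selected, and the sidedness is not stated.

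**The concern.** A significance test answers whether a difference has been shown. The hypothesis on rejection asks whether an increase has been ruled out. With very few events, non-significance is the likely result whether or not rejection has risen, so it carries little information about the second question. Section 10 avoids this problem for eGFR but not for rejection.

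The table adds to the risk. It lists 77 per group for 1% against 5%, so a reader would conclude that a trial with 83 per group has at least 80% power to detect that rise. If the planned test has far less power, a several-fold rise in rejection could be reported as no significant difference and taken as reassurance.

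**Working it through.** **Inputs.** 83 per arm (Section 8); reference rejection rate 1-2%, power 80% and alpha 0.05 (Section 10); follow-up 12 months (Section 8). No post-randomization dropout is stated, so none is assumed, which favours the trial.

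**Step 1: reproduce the rejection table.** Take non-inferiority with equal true rates p, the tabled difference d as margin, and one-sided alpha 0.05:

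n per arm = 2p(1-p)(1.645 + 0.842)² / d²

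For p = 0.01 and d = 0.04 this is 76.5, which rounds up to 77. For comparison, the table below also gives n for a two-sided 0.05 test of the two listed rates (pooled-variance formula), and the simulated power of a two-sided 0.05 log-rank at 83 per arm (6,000 runs, exponential times, 12 months).

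| Rates | Plan's n | Non-inferiority n | Two-sided test n | Log-rank power at 83 |
|---|---|---|---|---|
| 1% v 4% | 137 | 137 | 424 | 21% |
| 1% v 5% | 77 | 77 | 285 | 30% |
| 1% v 6% | 49 | 49 | 211 | 41% |
| 1% v 8% | 25 | 25 | 137 | 63% |
| 2% v 5% | 270 | 270 | 588 | 17% |
| 2% v 7% | 97 | 97 | 269 | 33% |
| 2% v 8% | 68 | 68 | 206 | 41% |
| 2% v 9% | 50 | 50 | 166 | 51% |

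All eight rows match the non-inferiority formula. No test-of-difference formula that was tried comes close. For 1% v 5%, an unpooled variance gives 282, a one-sided test 224, the Schoenfeld log-rank formula about 200 and the Freedman formula about 300, against the stated 77.

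**Step 2: expected events.** In the monthly arm, 83 × 0.01 = 0.8 and 83 × 0.02 = 1.7. Across the tabled scenarios the two arms together have about 4 (83 × 0.05) to 9 (83 × 0.11) rejections.

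**Step 3: power, second method.** With D total events and equal arms, approximate the log-rank by Z = (O - D/2) / √(D/4), where O is the number of events in the two-monthly arm. Enumerating binomial counts gives power of 31% for 1% v 5% and 16% for 2% v 5%, in line with the simulation. A doubling is declared significant 4% of the time from 1% and 10% from 2%.

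**Step 4: what a non-significant result leaves open** (83 per arm; p from step 3, Newcombe 95% interval for the two-monthly minus monthly difference).

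- 5 v 1: Z = (5 - 3) / √1.5 = 1.63, p = 0.10. The difference is 4.8 points, interval -1.5 to +12.2.
- 3 v 1: Z = (3 - 2) / √1 = 1.00, p = 0.32. The difference is 2.4 points, interval -3.4 to +9.0.
- 1 v 1: the difference is 0, interval -5.4 to +5.4.

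Miettinen-Nurminen score intervals are close: -1.2 to +12.3 for 5 v 1, -3.3 to +9.1 for 3 v 1, and ±5.4 for 1 v 1.

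**Step 5: what an interval judged against a margin could achieve.** With equal true rates, power is Φ(m/SE - 1.96), where SE = √(2p(1-p)/83) and the criterion is a two-sided 95% interval. At 1%, SE = 1.54 points and power is 49%, 74% and 90% for margins of 3, 4 and 5 points. At 2%, SE = 2.17 points and power is 28%, 45%, 63% and 79% for margins of 3, 4, 5 and 6 points. These are normal approximations and are rough at such low counts.

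**The case against.** Several points on the other side stand and limit the finding.

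- A reader might infer that Section 10 offers nothing but a p-value. It does not: rejection rates by arm at 6 and 12 months, Kaplan-Meier analyses and a comparison of severity are also planned. What is missing is an interval for the difference and a rule for interpreting it.
- A reader might infer that the plan commits to reading non-significance as no increase. No sentence says so. The formal primary objective (Section 2.1) concerns GFR only, and rejection is a secondary outcome that the study aims to compare. The misreading is a risk that the plan leaves open.
- A reader might extend the criticism in full to death and graft loss. The hypothesis makes no explicit no-increase statement for either, and no expected rates are given, so power cannot be computed for them.
- Rejection is also monitored during the trial. Section 4.4 sets review triggers (for example 7 and 15 of 83), and the DSMB charter sets others. These count events in the two-monthly arm only. They neither compare arms nor define what no increase means, so they do not fill the gap.
- A secondary outcome without its own margin is not in itself an error. A compulsory pass/fail bound would be a debatable choice, since step 5 shows that it could often fail even with equal rates.

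None of this supplies an interval for the rejection difference, or reconciles the table with the planned test.

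**Conclusion.** The concern holds for acute rejection. At 83 per arm and a 1-2% reference rate, the planned log-rank has about 30% power for 1% v 5% and about 16% for 2% v 5%. An observed 5 v 1 split would be non-significant while leaving an excess of about 12 points possible. Non-significance therefore cannot support the rejection half of the hypothesis.

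Separately, the rejection table and the analysis do not match. The table's 77 per group is a non-inferiority size for a 4-point margin at one-sided 0.05 with equal true rates. A two-sided test of 1% v 5% needs about 280 per group.

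The power figures assume a reference rate of 1-2%, equal follow-up and no dropout. The non-inferiority basis of the table is inferred from the exact match on all eight rows; the document does not state it. For death and graft loss, the point is confined to the absence of an interval.

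**What to change.** In Section 10:

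1. Make the main rejection result the 12-month two-monthly minus monthly difference with a two-sided 95% confidence interval, using a score-type method at these counts. Keep the log-rank as supporting.
2. State that a non-significant log-rank will not be read as no increase, and that the report will give the size of increase not excluded.
3. Relabel the rejection table as non-inferiority margins at one-sided 0.05 with equal true rates, or replace it with the power of the log-rank at 83 per arm.
4. If the sponsor wants to claim no increase, choose one of the tabled differences as a margin in advance and justify it. The choice is a clinical judgement and is optional for a secondary outcome.
5. Report graft loss and death as differences with confidence intervals in the same table, without a margin.

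This needs revised wording and one extra table, with no new patients or data. The downside is candour: even with one rejection in each arm, the upper limit is +5.4 points, so the report will probably have to concede that an increase of about 5 points or more is not excluded.
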